5.5 Withdrawal of Subjects and Discontinuation of Study

A subject may voluntarily withdraw from the study drug and/or study at any time. Subjects must be withdrawn from the study drug and/or study for reasons including, but not limited to, the following:

- The subject requests withdrawal from the study.
- The investigator believes it is in the best interest of the subject.
- Clinically significant abnormal laboratory results or AEs, which rule out continuation of the study drug, as determined by the investigator or the AbbVie Therapeutic Area (TA) Medical Director (MD).
- Subject is non-compliant with TB prophylaxis (if applicable) or develops active TB at any time during the study.
- Malignancy, except for localized NMSC or carcinoma in-situ of the cervix where discontinuation is at the discretion of the investigator.
- The subject becomes pregnant while on study drug.
- Eligibility criteria violation was noted after the subject started study drug and continuation of the study drug would place the subject at risk.
- Introduction of prohibited medications or dosages and continuation of the study drug would place the subject at risk.
- Subject is significantly noncompliant with study procedures, which would put the subject at risk for continued participation in the trial.
- Post-Baseline occurrence of one or more of the following hepatic test abnormalities (confirmed on a second separate sample at least 48 hours apart):
 - ALT or AST > 8 × ULN;
 - ALT or AST > 5 × ULN for more than 2 weeks;
 - ALT or AST > 3 × ULN and total bilirubin > 2 × ULN or international normalized ratio (INR) > 1.5;
 - ALT or AST > 3 × ULN with the appearance of fatigue, nausea, vomiting, right upper quadrant pain or tenderness, fever, rash, and/or eosinophilia (> 5%).
 - Subjects who meet any of the above criteria should be evaluated for an alternative etiology of the ALT or AST elevation and managed as medically appropriate. If applicable, the alternative etiology should be documented (in the eCRF if reported as an AE). If ALT or AST values return to the normal reference range or its Baseline value, study drug may be restarted. If restarting study drug, documentation should include reason that rechallenge is

expected to be safe. If after clinically appropriate evaluation, no alternative etiology for ALT or AST elevation is found or the ALT or AST elevation has not resolved or is not trending down toward normal, the subject should be discontinued from study drug.

For subjects to be considered lost to follow-up, reasonable attempts must be made to obtain information on the subject's final status. At a minimum, 2 telephone calls must be made and 1 certified letter must be sent and documented in the subject's source documentation.

AbbVie may terminate this study prematurely, either in its entirety or at any site. The investigator may also stop the study at his/her site if he/she has safety concerns. If AbbVie terminates the study for safety reasons, AbbVie will promptly notify the investigator.

COVID-19 Pandemic-Related Acceptable Protocol Modification

During the COVID-19 pandemic, it may be necessary to employ mitigation strategies to enable the investigator to ensure subject safety and continuity of care. Acceptable mitigation strategies are identified and included in the Operations Manual in Appendix F.

The investigator should contact the sponsor medical contact before discontinuing a subject from the study for a reason other than described in protocol to ensure all acceptable mitigation steps have been explored.

Refer to the Operations Manual in Appendix F for details on how to handle study activities/procedures.

Interruption/Discontinuation of Study Drug Due to COVID-19 Infection

For subjects with documented COVID-19, the timing of next administration of study drug or possibility of premature discontinuation from study drug should be discussed with the AbbVie Medical Contact. Follow subsequent protocol Section 5.6 for subjects who discontinued study drug.

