Infections, especially opportunistic infections, are a potential risk with immunomodulators. Subjects will be screened and monitored throughout the study for Areas of Safety Interest (ASI)/Safety Topics of Interest. Screening procedures are outlined in the Activity Schedule (Appendix D). In consideration of

the ASI, the following supplemental report form(s) must be completed if AEs in any of the following areas are reported during the study (Table 3).

Adverse Event	Supplemental Report
Cardiac events	Cardiovascular History and CV Risk Factors eCRF
Myocardial infarction or unstable angina	Cardiovascular (Cardiac) AE eCRF
Cerebral vascular accident	Myocardial Infarction and Unstable Angina AE eCRF
Cardiovascular death	Heart Failure AE eCRF
	Cerebral Vascular Accident and Transient Ischemic Attack AE eCRF
	Combination Thrombotic Event AE eCRF
	Arrhythmia AE eCRF
Discontinuation or interruption of study drug due to a: Hepatic-related AE Hepatic-related SAE ALT/AST > 8 × ULN or ALT/AST > 3 × ULN with a total bilirubin > 2 × ULN	Hepatic AE eCRF
Suspected anaphylactic/systemic hypersensitivity reactions	Hypersensitivity Reaction Signs and Symptoms eCRF
TB Subjects with events of latent TB or suspected TB after initiation of study drug should have a TB Supplemental Form completed.	TB Supplemental eCRF
Death	Death eCRF

AE = adverse event; CV = cardiovascular; eCRF = electronic case report form; SAE = serious adverse event; TB = tuberculosis

Adverse Event Severity and Relationship to Study Drug

Adverse events must be graded to the 5 criteria described in the National Cancer Institute (NCI) Common Terminology Criteria for Adverse Events (CTCAE) Version 5.0.²⁹

Grades: Grade refers to the severity of the AE. The CTCAE displays Grades 1 through 5 with unique clinical descriptions of severity for each AE based on this guideline:

- Grade 1 (Mild); Asymptomatic or mild symptoms; clinical or diagnostic observations only; intervention not indicated.
- Grade 2 (Moderate); Minimal, local, or noninvasive intervention indicated; limiting age-appropriate instrumental activities of daily living.
- Grade 3 (Severe); Medically significant but not immediately life-threatening; hospitalization or prolongation of hospitalization indicated; disabling; limiting self-care activities of daily living.

- Grade 4 (Severe); Life-threatening consequences; urgent intervention indicated.
- Grade 5 (Severe); Death related to AE.

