Appendix A. Protocol Deviations

The number and percentage of subjects who reported at least one of the following protocol deviation categories will be provided.

- Subject entered into the study even though s/he did not satisfy entry criteria.
- Subject developed withdrawal criteria during the study and was not withdrawn.
- Subject received wrong treatment or incorrect dose of study.
- Subject took prohibited concomitant medication.

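### Protocol 5.5 both permits restart and calls for discontinuation of study drug when liver enzymes normalise with no alternative cause found

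*Protocol*

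**What the plan says.** Protocol 5.5 opens its list of reasons with "Subjects must be withdrawn from the study drug and/or study for reasons including, but not limited to, the following". One entry is a set of four post-Baseline liver-test criteria, to be confirmed on a second sample:

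- "ALT or AST > 8 × ULN"
- "ALT or AST > 5 × ULN for more than 2 weeks"
- ALT or AST above 3 × ULN together with bilirubin above 2 × ULN or INR above 1.5
- ALT or AST above 3 × ULN with listed symptoms or eosinophilia

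A sub-bullet under that entry says what follows. The subject is evaluated for another cause. Then: "If ALT or AST values return to the normal reference range or its Baseline value, study drug may be restarted". Anyone restarting is to record why rechallenge is thought safe. The closing sentence says that if, after evaluation, "no alternative etiology for ALT or AST elevation is found or the ALT or AST elevation has not resolved", or the values are not heading down, study drug should be discontinued.

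Two other places depend on this entry. In Protocol 6.1, Table 3 asks for the Hepatic AE eCRF when drug is discontinued or interrupted for a hepatic AE or SAE, and it names the laboratory patterns "ALT/AST > 8 × ULN or ALT/AST > 3 × ULN with a total bilirubin > 2 × ULN". SAP Appendix A tabulates the deviation category "Subject developed withdrawal criteria during the study and was not withdrawn".

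**The concern.** The restart sentence turns only on the laboratory value. The discontinuation sentence turns on the cause as well as the value. A subject whose values resolve without an explanation meets the condition of both, and the section does not say which one governs. Two sites could treat the same subject in opposite ways, and each could point to the protocol.

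This is a safety instruction. Protocol 2.2 singles out liver laboratory changes for timely detection, evaluation and follow-up, and SAP 12.1 plans no data monitoring committee, so the site-level wording has to work without further interpretation.

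There is a smaller reporting consequence. The section does not say whether meeting a criterion under the withdrawal heading is a temporary interruption or a withdrawal. Several SAP summaries depend on that distinction: study drug discontinuation (Section 5.0), the compliance denominator (6.0), AEs leading to discontinuation (10.2.2 and 10.2.5) and the deviation category in Appendix A.

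**Working it through.** The plan states no figure on this point, so there is none to reproduce. The check lists the possible outcomes and sees which sentences apply to each.

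**Step 1. Outcomes.** After a confirmed criterion there are 2 cause states (alternative cause found or not) and 3 laboratory states (back to normal or Baseline; trending down but not resolved; neither). That gives 2 × 3 = 6 combinations. All six sit under the mandatory heading.

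**Step 2. Rules.**
- Restart permitted: values resolved. Cause is not a condition.
- Discontinue, reading L (literal): no cause, or not resolved, or not trending down. A resolved value is taken to satisfy the trend condition.
- Discontinue, reading N: no cause, or neither resolved nor trending down.
- Discontinue, reading A: no cause *and* neither resolved nor trending down. This replaces the first written *or* with *and*.

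**Step 3. Result.**

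| Cause | Laboratory course | Restart permitted | Discontinue (L) | Discontinue (N) | Discontinue (A) |
|---|---|---|---|---|---|
| Found | Resolved | yes | no | no | no |
| Found | Trending down | no | yes | no | no |
| Found | Neither | no | yes | yes | no |
| Not found | Resolved | **yes** | **yes** | **yes** | no |
| Not found | Trending down | no | yes | yes | no |
| Not found | Neither | no | yes | yes | yes |

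- Restart and discontinuation collide in 1 of 6 combinations: resolved, no cause found. This holds under L and N. It disappears only under A, which is not what is written. Reading A would also leave 3 of 6 combinations (found/trending, found/neither, not found/trending) with neither instruction.
- A second combination, cause found with values trending down but not resolved, changes with the reading: discontinue under L, no instruction under N.
- Restart is permitted in 2 of 6 combinations, although all six fall under the withdrawal heading. Whether that is a conflict depends on whether the heading means a temporary or a permanent stop, which is not stated.

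**Step 4. Table 3 against Section 5.5.** Splitting the third criterion into its bilirubin and INR arms gives five triggers.

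| Section 5.5 trigger | Named numerically in Table 3 |
|---|---|
| > 8 × ULN | yes |
| > 5 × ULN for more than 2 weeks | no |
| > 3 × ULN with bilirubin > 2 × ULN | yes |
| > 3 × ULN with INR > 1.5 | no |
| > 3 × ULN with symptoms or eosinophilia | no |

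The match is 2 of 5. The other three reach the form only through the hepatic AE and SAE lines. Under Protocol 6.1 a laboratory change counts as an AE only if it ends study participation, needs treatment, or the investigator judges it to be one. Section 5.6 asks subjects who stop drug to stay in follow-up, so stopping drug alone does not make the abnormality an AE. A laboratory-only stop that is not recorded as an AE could therefore lack the form.

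**The case against.** The strongest reply is that the sub-bullet is a coherent sequence: stop, evaluate, then restart or discontinue. Speaking of a restart presupposes an earlier stop, the heading does not say that the stop is permanent, and Table 3 mentions interruption, so a temporary hold seems to have been foreseen. Restart is optional and needs a documented safety reason. The closing sentence advises discontinuation without making it mandatory and could be read as limiting the earlier permission. A site that discontinues breaches neither sentence.

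Much of this stands, and it rules out three stronger readings that a reader might infer:

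- *That the withdrawal heading flatly contradicts the restart permission.* The stop-then-decide sequence is a natural reading. What remains is that the text never says so.
- *That Table 3 adds to the opposing instructions.* It decides when a form is completed and says nothing about stopping or restarting drug. Its row also includes hepatic AEs and SAEs, so it is not blind to the unnamed patterns. The symptoms in the fourth criterion would often be AEs in their own right.
- *That a subject restarted under Section 5.5 is automatically a deviation under SAP Appendix A.* That follows only if withdrawal means permanent withdrawal. If the initial stop counts, the subject was withdrawn and then restarted as the protocol allows.

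The reply does not resolve the case of values resolved with no cause found. The documented reason for rechallenge carries no condition about cause, and nothing ranks the two sentences.

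**Conclusion.** The inconsistency is real and narrow. Under either reading that keeps the written *or*, one of six combinations receives both a permission to restart and an instruction to discontinue. A second combination is unclear, and the nature of the initial stop is undefined. The Table 3 mismatch (2 of 5 triggers named) is a secondary data-capture gap, limited to laboratory-only stops that are not recorded as AEs.

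The documents give no expected number of hepatic cases; it is probably small. No sample size, power or type I error figure changes. The composite strategy in SAP 8.0 concerns only discontinuation for lack of efficacy, so the primary estimand is untouched. The point deserves correction because it governs a safety action.

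Two limits apply. The Operations Manual (Protocol Appendix F) is not in the text reviewed and may say more, though it would not remove the conflicting protocol sentences. Table 3 was read from a flattened layout, so it is uncertain whether its numeric thresholds stand alone or apply only when drug is stopped or interrupted.

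**What to change.** Rewrite the hepatic sub-bullet in Protocol 5.5 so that each of the six combinations of cause and laboratory course leads to one stated action, and say whether the initial stop is an interruption or a withdrawal. Which action belongs to which combination is for the sponsor's medical team.

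Then carry the result through. State in SAP Appendix A whether a subject restarted under the rule counts as a deviation, and use the same definition in the disposition, compliance and AE-leading-to-discontinuation summaries. Align Table 3's laboratory thresholds with the Section 5.5 triggers, so that completing the Hepatic AE eCRF does not depend on whether the abnormality was recorded as an AE.

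The cost is protocol wording, an eCRF trigger update and a short SAP clarification. No visits, tests or subjects are added.

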5.6 Follow-Up After Subject Discontinuation of Study Drug or from Study

To minimize missing data for safety and efficacy assessments, subjects who prematurely discontinue study drug treatment should continue to be followed for all regularly scheduled visits, unless subjects have decided to discontinue the study participation entirely (withdrawal of informed consent). Subjects should be advised on the continued scientific importance of their data even if they discontinue treatment with study drug early.

If a subject prematurely discontinues study participation, the procedures outlined for the PD visit should be completed as soon as possible, preferably within 2 weeks. In addition, if subject is willing, a follow-up phone call 140 days after the last dose of study drug may be completed to ensure all treatment-emergent AEs/serious adverse events (SAEs) have been resolved. The 140-day follow-up phone call following the last dose administration of risankizumab study drug during the trial will not be required for any subject who initiates commercially available risankizumab after completion of the Week 52 visit or premature discontinuation visit.

If a subject withdraws from study follow-up or withdraws permission for the collection of their personal data, the study staff may still use available public records to obtain information about survival status only, as appropriate per local regulations.

In the event a subject withdraws consent from the clinical study, biomarker research will continue unless the subject explicitly requests analysis to be stopped. When AbbVie is informed the subject has withdrawn and no longer wishes biomarker sample research to continue, samples will not be analyzed, and no new biomarker analysis data will be collected for the withdrawn subject or added to the existing data or database(s). A subject may withdraw consent for optional biomarker research at any time and remain in the clinical study. Data generated from clinical study and/or optional biomarker research, before subject withdrawal of consent, will remain part of the study results.

5.7 Study Drug

AbbVie will provide study drug for risankizumab or matching placebo. AbbVie-provided study drug should not be substituted or alternately sourced unless otherwise directed by AbbVie. Information about the study drug and placebo used in this study is presented in Table 2.

During Period A (Double-Blind Period), study site staff will administer study drug subcutaneously (risankizumab 150 mg or matching placebo in a pre-filled syringe [PFS]) at Baseline and Week 4 visits. Subjects will be trained by site staff on self-injection at the Baseline visit to proactively be prepared for at-home dosing by the subject or caregiver at Weeks 4, 28, and 40, should the need for a virtual visit arise due to COVID-19-related restrictions. Subjects may be retrained on self-injection at the Week 16 visit.

During Period B (Open-Label Period), study site staff will administer risankizumab as a 150 mg SC dose $(1 \times 150 \text{ mg PFS})$ at Week 16, Week 28, and Week 40 visits.

Only subjects who self-administer study drug at home due to COVID-related visit modifications (e.g., virtual visit) will record the self-administered dosing in a subject dosing diary.

Route of **Study Drug Dosage Form** Strength Administration Manufacturer Risankizumab (ABBV-066) Solution for 150 mg Active, SC injection AbbVie Biotechnology injection in PFS 150 mg/mL Ltd., Barceloneta, Puerto Rico Placebo for Risankizumab Solution for AbbVie Deutschland Not applicable SC injection (ABBV-066) injection in PFS GmbH & Co. KG,

Table 2. **Description of Study Drug and Placebo**

PFS = pre-filled syringe; SC = subcutaneous

Blinded risankizumab or placebo and open-label risankizumab will be packaged in quantities sufficient to accommodate study design. Each kit will be labeled per local requirements and this label must remain affixed to the kit. Upon receipt, study drug must be kept protected from light in the original packaging,

Ludwigshafen, Germany

in a refrigerator between 2°C to 8°C (36°F to 46°F). A temperature log must be maintained for documentation. Study drug must be kept in a secure location and must not be frozen at any time. Each kit will contain a unique kit number. This kit number is assigned to a subject via interactive response technology (IRT) and encodes the appropriate study drug to be dispensed at the subject's corresponding study visit. Upon receipt of the study drugs, the site will acknowledge receipt within the IRT system. All blank spaces on the label will be completed by the site staff prior to dispensing to subjects.

AbbVie will not supply drug other than risankizumab and matching placebo, and study drug will only be used for the conduct of this study. AbbVie-provided study drug should not be substituted or alternately sourced unless otherwise directed by AbbVie. If a subject is unable to come to the study site to pick up their study drug due to COVID-19, a direct-to-patient (DTP) study drug shipment can be made from the study site to the subject if allowed by local regulations. AbbVie will submit any required notifications to the regulatory authority as applicable. Refer to the Operations Manual in Appendix F for details on DTP shipment of study drug.

5.8 Randomization/Drug Assignment

All subjects will be assigned a unique identification number by the IRT at the Screening visit. For subjects who rescreen, the screening number assigned by the IRT at the initial Screening visit should be used. The IRT will assign a randomization number that will encode the subject's treatment group assignment according to the randomization schedule generated by Data and Statistical Sciences (DSS) at AbbVie.

Eligible subjects will be centrally randomized in a 1:1 ratio to risankizumab 150 mg or placebo groups during Treatment Period A. The randomization will be stratified by Baseline ppIGA ("moderate" [3] versus "severe" [4]) and Baseline BSA (< 10% versus \geq 10%). All subjects will receive risankizumab 150 mg during Treatment Period B.

All AbbVie personnel with direct oversight of the conduct and management of the study (with the exception of AbbVie Drug Supply Management Team) will remain blinded until the Primary Analysis at Week 16 is available. The investigator, study site personnel, and the subject will remain blinded to each subject's treatment throughout the study. To maintain the blind, the risankizumab PFS and placebo PFS provided for the study will be identical in appearance. The IRT will provide access to unblinded subject treatment information in the case of a medical emergency.

In the event of a medical emergency in which the investigator believes that knowledge of study drug treatment is required, reasonable efforts must be made to contact the AbbVie emergency contact prior to breaking the blind, as long as it does not compromise subject safety. However, if an urgent therapeutic intervention is necessary which warrants breaking the blind prior to contacting the AbbVie emergency contact, the investigator can directly access the IRT system to break the blind without AbbVie agreement. The date and reason that the blind was broken must be recorded in the source documentation and eCRF, as applicable.

5.9 Protocol Deviations

AbbVie does not allow intentional/prospective deviations from the protocol except when necessary to eliminate an immediate hazard to study subjects. The investigator is responsible for complying with all protocol requirements, written instructions, and applicable laws regarding protocol deviations. If a protocol deviation occurs (or is identified, including those that may be due to the COVID-19 pandemic), the investigator is responsible for notifying IEC/IRB, regulatory authorities (as applicable), and AbbVie.

6 SAFETY CONSIDERATIONS

6.1 Complaints and Adverse Events

Complaints

A complaint is any written, electronic, or oral communication that alleges deficiencies related to the physical characteristics, identity, quality, purity, potency, durability, reliability, safety, effectiveness, or performance of a product/device. Complaints associated with any component of this investigational product must be reported to AbbVie.

Product Complaint

A product complaint is any complaint related to the biologic or drug component of the product or to the medical device component(s).

For a product this may include, but is not limited to, damaged/broken product or packaging, product appearance whose color/markings do not match the labeling, labeling discrepancies/inadequacies in the labeling/instructions (e.g., printing illegible), missing components/product, device not working properly, or packaging issues.

Product complaints concerning the investigational product and/or device must be reported to AbbVie within 24 hours of the study site's knowledge of the event. Product complaints occurring during the study will be followed-up to a satisfactory conclusion.

Medical Complaints/Adverse Events and Serious Adverse Events

An AE is defined as any untoward medical occurrence in a subject or clinical investigation subject administered a pharmaceutical product and which does not necessarily have a causal relationship with this treatment. An AE can therefore be any unfavorable and unintended sign (including an abnormal laboratory finding), symptom, or disease temporally associated with the use of a medicinal (investigational) product, whether or not the event is considered causally related to the use of the product.

Such an event can result from use of the drug as stipulated in the protocol or labeling, as well as from "special situations" such as accidental or intentional overdose, medication error, occupational or accidental exposure, off-label use, drug abuse, drug misuse, or drug withdrawal, all which must be reported whether associated with an AE or not. Any worsening of a pre-existing condition or illness is considered an AE. Worsening in severity of a reported AE should be reported as a new AE. Laboratory

abnormalities and changes in vital signs are considered to be AEs only if they result in discontinuation from the study, necessitate therapeutic medical intervention, and/or if the investigator considers them to be AEs.

The investigators will monitor each subject for clinical and laboratory evidence of AEs on a routine basis throughout the study. All AEs will be followed to a satisfactory conclusion.

An elective surgery/procedure scheduled to occur during a study will not be considered an AE if the surgery/procedure is being performed for a pre-existing condition and/or the surgery/procedure has been pre-planned prior to study entry. However, if the pre-existing condition deteriorates unexpectedly during the study (e.g., surgery performed earlier than planned), then the deterioration of the condition for which the elective surgery/procedure is being done will be considered an AE.

If an AE, whether associated with study drug or not, meets any of the following criteria, it is to be reported to AbbVie clinical pharmacovigilance or contract research organization (CRO) (as appropriate) as an SAE within 24 hours of the site being made aware of the serious SAE (refer to Section 4.3 of the Operations Manual for reporting details and contact information):

Death of Subject	An event that results in the death of a subject.
Life-Threatening	An event that, in the opinion of the investigator, would have resulted in immediate fatality if medical intervention had not been taken. This does not include an event that would have been fatal if it had occurred in a more severe form.
Hospitalization or Prolongation of Hospitalization	An event that results in an admission to the hospital for any length of time or prolongs the subject's hospital stay. This does not include an emergency room visit or admission to an outpatient facility.
Congenital Anomaly	An anomaly detected at or after birth, or any anomaly that results in fetal loss.
Persistent or Significant Disability/Incapacity	An event that results in a condition that substantially interferes with the activities of daily living of a study subject. Disability is not intended to include experiences of relatively minor medical significance such as headache, nausea, vomiting, diarrhea, influenza, and accidental trauma (e.g., sprained ankle).

Important Medical Event Requiring Medical or Surgical Intervention to Prevent Serious Outcome An important medical event that may not be immediately life-threatening or result in death or hospitalization, but based on medical judgment may jeopardize the subject and may require medical or surgical intervention to prevent any of the outcomes listed above (i.e., death of subject, life-threatening, hospitalization, prolongation of hospitalization, congenital anomaly, or persistent or significant disability/incapacity). Additionally, any elective or spontaneous abortion or stillbirth is considered an important medical event, along with any suspected transmission of an infectious agent via a medicinal product if no other serious criterion is applicable. Examples of such events include allergic bronchospasm requiring intensive treatment in an emergency room or at home, blood dyscrasias or convulsions that do not result in inpatient hospitalization, or the development of drug dependency or drug abuse.

All AEs reported from the time of study drug administration until 140 days (20 weeks) after discontinuation of study drug administration will be collected, whether solicited or spontaneously reported by the subject. In addition, study procedure-related serious and nonserious AEs will be collected from the time the subject signs the study-specific informed consent.

The following definitions will be used for Serious Adverse Reaction (SAR) and Suspected Unexpected Serious Adverse Reaction (SUSAR):

- SAR Defined as all noxious and unintended responses to an Investigational Medicinal Product (IMP) related to any dose administered that result in an SAE as defined above.
- SUSARRefers to individual SAE case reports from clinical trials where a causal
relationship between the SAE and the IMP was suspected by either the sponsor
or the investigator, is not listed in the applicable Reference Safety Information
(RSI), and meets one of the above serious criteria. All individually reported SARs
are considered suspected.

AbbVie will be responsible for SUSAR reporting for the IMP in accordance with global and local requirements.

Adverse events will be monitored throughout the study to identify any of special interest that may indicate a trend or risk to subjects.

Areas of Safety Interest/Safety Topics of Interest

Infections, especially opportunistic infections, are a potential risk with immunomodulators. Subjects will be screened and monitored throughout the study for Areas of Safety Interest (ASI)/Safety Topics of Interest. Screening procedures are outlined in the Activity Schedule (Appendix D). In consideration of

the ASI, the following supplemental report form(s) must be completed if AEs in any of the following areas are reported during the study (Table 3).

Adverse Event	Supplemental Report
Cardiac events	Cardiovascular History and CV Risk Factors eCRF
Myocardial infarction or unstable angina	Cardiovascular (Cardiac) AE eCRF
Cerebral vascular accident	Myocardial Infarction and Unstable Angina AE eCRF
Cardiovascular death	Heart Failure AE eCRF
	Cerebral Vascular Accident and Transient Ischemic Attack AE eCRF
	Combination Thrombotic Event AE eCRF
	Arrhythmia AE eCRF
Discontinuation or interruption of study drug due to a: Hepatic-related AE Hepatic-related SAE ALT/AST > 8 × ULN or ALT/AST > 3 × ULN with a total bilirubin > 2 × ULN	Hepatic AE eCRF
Suspected anaphylactic/systemic hypersensitivity reactions	Hypersensitivity Reaction Signs and Symptoms eCRF
TB Subjects with events of latent TB or suspected TB after initiation of study drug should have a TB Supplemental Form completed.	TB Supplemental eCRF
Death	Death eCRF

AE = adverse event; CV = cardiovascular; eCRF = electronic case report form; SAE = serious adverse event; TB = tuberculosis

Adverse Event Severity and Relationship to Study Drug

Adverse events must be graded to the 5 criteria described in the National Cancer Institute (NCI) Common Terminology Criteria for Adverse Events (CTCAE) Version 5.0.²⁹

Grades: Grade refers to the severity of the AE. The CTCAE displays Grades 1 through 5 with unique clinical descriptions of severity for each AE based on this guideline:

- Grade 1 (Mild); Asymptomatic or mild symptoms; clinical or diagnostic observations only; intervention not indicated.
- Grade 2 (Moderate); Minimal, local, or noninvasive intervention indicated; limiting age-appropriate instrumental activities of daily living.
- Grade 3 (Severe); Medically significant but not immediately life-threatening; hospitalization or prolongation of hospitalization indicated; disabling; limiting self-care activities of daily living.

- Grade 4 (Severe); Life-threatening consequences; urgent intervention indicated.
- Grade 5 (Severe); Death related to AE.

If no specific criteria per CTCAE Version 5 guidelines are available for the reported event, the event should be graded per the investigator's judgment according to the definitions outlined above.

The investigator will use the following definitions to assess the relationship of the AE to the use of study drug:

Reasonable Possibility	After consideration of factors including timing of the event, biologic plausibility, clinical judgment, and potential alternative causes, there is sufficient evidence (information) to suggest a causal relationship.
No Reasonable Possibility	After consideration of factors including timing of the event, biologic plausibility, clinical judgment, and potential alternative causes, there is insufficient evidence (information) to suggest a causal relationship.

Pregnancy

While not an AE, pregnancy in a study subject must be reported to AbbVie within 24 hours after the site becomes aware of the pregnancy. Subjects who become pregnant during the study must be discontinued (Section 5.5). If a pregnancy occurs in a study subject, information regarding the pregnancy and the outcome will be collected.

The pregnancy outcome of an elective or spontaneous abortion, stillbirth, or congenital anomaly is considered an SAE and must be reported to AbbVie within 24 hours after the site becomes aware of the event.

